### **10.4** Serious Adverse Event Definition

A serious adverse event is an event that is: (a) fatal, (b) life-threatening (c) results in persistent or significant disability/incapacity (d) requires or prolongs in subject hospitalization or (e) leads to a congenital anomaly or birth defect.

Life threatening is defined as an event in which the subject is at risk of death at the time of the event. It does not refer to an event that hypothetically might have caused death if it was more severe.

Disability is defined as a substantial disruption of a person's ability to conduct normal life functions.

An unexpected adverse event is one that has not been previously observed or one that is a specificity or severity not consistent with the current investigator brochure.

All pre-existing medical conditions will be recorded on medical history or physical exam case report forms.

Hospitalization or prolonged hospitalization for diagnostic or elective procedures for pre-existing conditions will not be considered as SAE. Exceptions of adverse device effects are changes related to the underlying disease or medical conditions that are consistent with expected disease progression and will not be considered adverse device effects in this study.

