# 8.1.2 Implantation

Implantation day will be recorded as day 0; enrolment day Safety data will be collected upon enrolment.

Patients will be hospitalized as decided by the surgeon, estimated 1 hospitalization day will be required. Patients will be informed that they have the right to contact the PI or designee per their discretion

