#### 10.5 Unanticipated Adverse Device-related Event Definition

An unanticipated adverse device-related event is any serious adverse effect on health or safety, any life-threatening problem or death caused by, or associated with a device, if that effect, problem, or death was not previously identified in nature, severity, or degree of incidence in section Known Potential Risks.

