# **10.9.2 Device Explantation Procedure**

Upon reaching the decision to remove the device, the surgeon may choose one of the following surgical approaches according to the specific ocular condition and per his/her discretion:

- 1) Releasing the skirt component from under the overlying conjunctiva using sharp dissection.
- Removal of only the optic component of the CorNeat KPro while the skirt component remains under the overlying conjunctiva. This will be performed by cutting the skirt around the optic componenet with an appropriate blade or scissors throughout the entire circumference.

The eye will be implanted with either a replacement CorNeat KPro, tectonic corneal graft or an alternative artificial cornea.

It should be noted that in severe cases of the above-mentioned complications, evisceration or enucleation might be the only options remaining.

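### The serious adverse event definition in 10.4 has no criterion for harm to the eye, so removal of the device or the eye without admission can be recorded as non-serious

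*Protocol*

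**What the plan says.** Section 10.4 gives five criteria. The first two are death and threat to life, the next two read "results in persistent or significant disability/incapacity (d) requires or prolongs in subject hospitalization", and the fifth is a birth defect. The list ends there. It has no further item for medically important events, for permanent impairment of a body structure, or for intervention to prevent such impairment. The disability item is then narrowed: "Disability is defined as a substantial disruption of a person's ability to conduct normal life functions".

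Section 10.9.1 gives three routes to removal of the device: severe retroprosthetic membrane, infection and tissue necrosis. Section 10.9.2 adds that in severe cases "evisceration or enucleation might be the only options remaining". Neither section says whether these outcomes are serious.

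Section 10.5 defines an unanticipated adverse device-related event (UADE) through "any serious adverse effect on health or safety", a life-threatening problem or death, provided it was not already identified in section 10.8 (Known Potential Risks).

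The only statement on admission concerns the implantation itself (8.1.2): "Patients will be hospitalized as decided by the surgeon", with one day estimated.

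**The concern.** This is a first-in-human implant in the eye, and the gravest local harm it can do is loss of the device or of the eye. The seriousness list does not name that harm. It can be serious only through the person-level disability item or through admission.

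Section 7.1 admits subjects with unilateral corneal blindness, and 7.2.1.7 asks only for light perception in the study eye. A subject who relies on a good fellow eye could lose the study eye with little change in daily function. Admission would then decide the label, so the same harm could be serious in one subject and non-serious in another.

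Three things in the protocol depend on the label: the Serious Adverse Event Report Form (Synopsis, Safety management), the reported incidence and nature of serious events (Synopsis, Safety Assessment), and in part the notices to other investigators (10.7). Investigators apply the definition as events occur, so it cannot be put right at analysis.

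**Working it through.** The protocol states no figure on this point, so the check applies the definitions to a case. Take a subject with unilateral disease, a functioning fellow eye and no regained vision, whose device or eye is removed without admission.

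**Against 10.4:**
1. Fatal: no.
2. Life-threatening: no.
3. Disability or incapacity: arguable. The test is the person's normal life functions, which the fellow eye may still carry.
4. Hospitalisation: no, by construction of the case.
5. Birth defect: no.

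No item is clearly met, so a non-serious classification is consistent with the text. If vision was regained, or the disease is bilateral, item 3 is easier to meet. If the subject is admitted, item 4 is met. The gap is therefore confined to a subset.

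**Against 10.5:** two conditions must hold.
1. Serious: open. The only definition of seriousness in the protocol is in 10.4, although 10.5 does not refer to it.
2. Not already identified in 10.8: usually fails. Section 10.8 lists retroprosthetic membrane, endophthalmitis, corneal melt and lack of retention, which between them cover the three routes in 10.9.1. Evisceration and enucleation appear in 10.9 but not in 10.8, so for them an argument from severity remains.

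Most such events would thus not be UADEs even if 10.4 were repaired.

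**What still captures the event:**
- 10.1: every adverse event is recorded.
- 10.7: any device-related event goes to the sponsor through the EDC system, serious or not.
- 5.2.1: the primary safety endpoint counts treatment-related adverse events as well as UADEs.
- 5.2.2: device retention is the primary effectiveness endpoint.
- 10.11: the stopping rule depends on severity and device removal, not on seriousness.

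**Size:**
- One misclassified subject among 10: 1/10 = 10 percentage points of serious-event incidence.
- Expected device losses in one year at the 6% Boston KPro non-retention figure in 10.8: 10 × 0.06 = 0.6. This counts all losses, not misclassified ones.
- Expected misclassified losses: 0.6 × s, where s is the share handled without admission and not judged disabling. The protocol gives no value for s. Between s = 0 and s = 1 the result runs from 0 to 0.6.

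**The case against.** The strongest reply is that only a label is at stake. The event is recorded, reaches the sponsor if device-related, enters the primary safety endpoint if treatment-related, and counts against retention if the device is lost. The safety board in 10.10 reviews the data and is not limited to serious events. No success threshold is attached to serious-event incidence. The Synopsis also says that reporting follows GCP, ISO 14155:2011 and local regulations.

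Most of this stands, and it limits the point. Three stronger readings that a reader might infer are not supported:
- **That the primary safety endpoint misses these events.** Its treatment-related component includes them. The effect on the UADE component is small, because most causes are already listed in 10.8.
- **That the protocol envisages explantation or evisceration as day surgery.** Section 8.1.2 concerns implantation only, and 10.9.1 describes the care of infection as urgent. No admission practice for removal is stated either way.
- **That 2 to 3 device losses in 10 should be expected within a year.** In 10.8 the one-year non-retention figure is 6%. The 25% figure is at five years, and the 30% figure is for corneal melt.

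The reply does not remove the gap itself. The form, the incidence tables and part of the notification still depend on the word serious. Severity is not a full substitute, because 10.2 grades it by discomfort and limits on daily life, which is again a person-level scale. Whether the cited standards close the gap in practice cannot be judged from the protocol. The text that investigators have before them is 10.4.

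**Conclusion.** The point holds as a gap in classification. Under 10.4, removal of the device or of the study eye may be recorded as non-serious when it is done without admission, mainly in unilateral disease with a functioning fellow eye and no regained vision. Serious-event incidence is then understated by 10 percentage points per subject among 10, and the serious-event form and serious-event notification may not be triggered. The effect on UADE counts is limited, and the events stay visible elsewhere in the safety and retention data.

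This rests on two assumptions: that the five items are read as complete, as they are written, and that some removals take place without admission. The protocol is silent on the second, so the frequency is unknown. The change is worth making because the harm concerned is the main one to the treated organ and the repair is cheap.

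**What to change.** Add one sentence to 10.4: an event is also serious if it results in permanent impairment or loss of the study eye or of its light perception, or needs medical or surgical intervention to prevent this (including device removal or exchange, evisceration or enucleation), whether or not the subject is admitted. Add the same criterion to the seriousness field of the eCRF, so that all sites apply it alike.

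This alters how events are classified and leaves clinical management untouched. The cost is a short amendment, an eCRF update and a possibly higher serious-event count.

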# 8.1.6 Follow Up

Follow Up- (up to 12 months) visit schedule: One day post op, one week ( $\pm$ 2 days) one month ( $\pm$ 7 days), two months ( $\pm$ 14 days) three months ( $\pm$ 14 days), six months ( $\pm$ 14 days), nine months ( $\pm$ 14 days) and twelve-months ( $\pm$ 14 days) post-surgery.

On each follow-up visit, subjects will be subjected to the following examinations: (i) slit-lamp biomicroscopy, (ii) visual acuity (BCVA), (iii) IOP, (iv) concomitant medications record, (v) Pain assessment and (vi) Adverse events recording.

In every follow up visit, IOP will be measured by tactile assessment as follows: Digital palpation of the globe will be performed with the patient gently looking down. Palpation directly over a glaucoma drainage device plate should be avoided in patients with tubes who should be instructed to look in an alternate direction. The eye should then be very gently balloted between the surgeon's two index fingers, as his or her other fingers rest against the face and orbital rim.

In addition, OCT/UBM imaging will be performed on screening visit, on 1-week post-op and every 3 months starting at 3 months post-surgery.

During all study period only safety data (i.e. possibly related or related AEs, SAEs, UADE) will be collected in the eCRF for visits performed outside of protocol visits timetable.

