# **10 Safety Parameter**

# **10.1** Adverse Event Definition

An adverse event is any undesirable or unintentional event that occurs during the course of the study, whether or not considered related to the device. Regardless of severity or relationship to the investigational device, all adverse events occurring during the study must be recorded in the subject's CRF

All adverse events will be coded using the Medical Dictionary for Regulatory Activities (MedDRA, most updated version) terminology and presented in tables by System Organ Class (SOC) and Preferred Term (PT).

AE data will be listed individually and summarized by SOC and by PT within a system organ class.

Additional tables will present adverse events by PT, SOC and severity and by relatedness to study device.

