### 10.8 Known Potential Risks

Known risks from usage of similar artificial corneas are:

- Postoperative Corneal Melt is one of the most severe complications that can occur after keratoprosthesis surgery with incidence of up to 30%. It may lead to scarring, irregular astigmatism, photophobia, decreased vision, and even endophthalmitis.
- Lack of graft retention Corneal grafts tissue artificial integration is limited and with time the bond between the implant and eye weakens. E.g. Boston KPro's retention rates decreases over time with incidence of lack of retention of 6, 11 and 25% after 1, 2- and 5-years post-op, respectively.
- Post-operative Glaucoma is the most important threat to long-term preservation of vision following Boston KPro surgery with elevation of intraocular pressure in 19–38 % of patients postoperatively and progression of pre-operative glaucoma in 7–14 % of patients. Development of glaucoma de novo following Kpro placement has been reported in 2-28% of KPro recipients .
- Poor post-operative visual quality Eyes with current KPros have very limited visual field and poor visual function. About 50% of patients implanted with Boston KPro maintain 20/200 CDVA after 8 years from surgery .

<sup>6 Bouhout, S., Robert, M.C., Deli, S. and Harissi-Dagher, M., 2018. Corneal melt after Boston keratoprosthesis: Clinical presentation, management, outcomes and risk factor analysis. Ocular immunology and inflammation, 26(5), pp.693-699.

<sup>7 Schaub, F., Bachmann, B.O., Seyeddain, O., Moussa, S., Reitsamer, H.A. and Cursiefen, C., 2017. Mid-and longterm experiences with the Boston-keratoprosthesis. The Cologne and Salzburg Perspective. Klinische Monatsblatter fur Augenheilkunde, 234(6), p.770.

<sup>8 Jin, B. and Zhu, X., 2017. The pathogenesis and prevention of corneal graft melting after keratoplasty. J Clin Ophthalmol, 1(1), p.10.

<sup>9 Ciolino, J.B., Belin, M.W., Todani, A., Al-Arfaj, K., Rudnisky, C.J. and Boston Keratoprosthesis Type 1 Study Group, 2013. Retention of the Boston keratoprosthesis type 1: multicenter study results. Ophthalmology, 120(6), pp.1195-1200.

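### Section 10.4 takes SAE status away from elective or diagnostic admissions for pre-existing conditions, with no exception for a condition that worsened after implantation, so SAE incidence may be undercounted

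*Protocol*

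**What the plan says.** Protocol section 10.4 lists five criteria for a serious adverse event. The hospitalisation criterion reads "d) requires or prolongs in subject hospitalization". Later in the same section comes the exemption: "Hospitalization or prolonged hospitalization for diagnostic or elective procedures for pre-existing conditions will not be considered as SAE". The sentence after it sets a second exception, "Exceptions of adverse device effects are changes related to the underlying disease or medical conditions that are consistent with expected disease progression", and says that such changes do not count as adverse device effects.

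Four other places bear on the point:

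- The Safety Assessment paragraph of the synopsis (section 3) names the incidence and nature of SAEs as data to be collected from the implantation visit onward.
- Section 10.5 builds on seriousness: "An unanticipated adverse device-related event is any serious adverse effect on health or safety". Life-threatening problems and deaths also qualify. In every case the effect must not already be identified in nature, severity or degree of incidence in section 10.8.
- Section 10.1 requires full recording: "Regardless of severity or relationship to the investigational device, all adverse events occurring during the study must be recorded in the subject's CRF".
- Section 12.2.3 says that no separate SAP is in use, so the definition in 10.4 is the operative one.

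**The concern.** An exemption for admissions linked to old conditions is meant to keep events that have nothing to do with the trial out of the SAE count. It does that only if it stops applying once the condition worsens on study. Section 10.4 sets no such limit. Its wording turns on two things: whether the condition existed before, and whether the procedure is elective or diagnostic. Whether the admission was caused by a deterioration after the device went in plays no part.

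This matters more here than in most trials. All subjects have pre-existing disease of the eye that receives the device, so a complication can easily present as worsening of something already in the medical history. For a complication confined to one eye, death, threat to life and congenital anomaly will rarely apply, and the disability criterion needs a substantial disruption of normal functioning. Hospitalisation is then often the criterion that decides seriousness, and it is the one the exemption removes.

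At stake is the SAE count of a ten-subject first-in-human safety study, and with it the step at which an event is checked against the UADE definition.

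**Working it through.** The protocol gives no figure for this point, so there is nothing to reproduce. The check is a reading of the passages side by side, followed by a short calculation of scale.

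**Step 1: does any limit on worsening apply to the exemption?** The only limiting phrase nearby is the reference to expected disease progression in the next sentence ("Exceptions of adverse device effects are changes related to the underlying disease or medical conditions that are consistent with expected disease progression"). Its subject is adverse device effects, not SAE status. The exemption itself carries no limit on when the procedure was planned or whether the condition changed. The protocol does not say outright that worsened conditions are exempt; that follows from the missing limit.

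**Step 2: can the situation arise in this population?** Section 7.1 enrols subjects with corneal blindness, so each study eye has pre-existing disease. Section 7.2.2.4 excludes only end-stage glaucoma. Section 8.1.6 gives instructions for eyes with glaucoma drainage devices, so such eyes are expected. Section 10.8 cites, for a similar device, "progression of pre-operative glaucoma in 7–14 % of patients".

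**Step 3: apply the rule to a case.** A subject with pre-operative glaucoma worsens after implantation and is admitted electively for it. The worsening is an adverse event under 10.1. It meets the hospitalisation criterion, but the condition is pre-existing and the procedure elective, so 10.4 takes SAE status away. It remains serious only if another criterion is met.

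**Step 4: follow the case downstream.**

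- *SAE incidence (synopsis):* the case is not counted.
- *UADE (10.5):* apart from life-threatening problems and death, the effect must be serious. The protocol defines seriousness only in 10.4. A worsening beyond the severity or incidence listed in 10.8 could be a UADE, but once it is classed as non-serious it may not be examined as one.
- *Primary safety endpoint (5.2.1):* treatment-related adverse events count whether or not they are serious, so a related case is kept.
- *Sponsor reporting (10.7):* device-related events are reported whether or not they are serious.
- *Unscheduled visits (8.1.6):* "During all study period only safety data (i.e. possibly related or related AEs, SAEs, UADE) will be collected in the eCRF for visits" outside the timetable. A case judged unrelated and seen only at such a visit is not on that list once it loses SAE status, although 10.1 requires every adverse event to be recorded.

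**Step 5: scale.** One subject in ten is 1/10 = 10 percentage points of the SAE proportion. The number of SAEs lost through glaucoma alone would be 10 × p × h, where p is the probability of progression and h is the share of those cases admitted electively and not serious on another criterion. If the 7–14% range in 10.8 applied to all ten subjects over the trial, 10 × p would be 10 × 0.07 = 0.7 to 10 × 0.14 = 1.4. The protocol gives no value for h. Letting h run from 0 to 1 gives anything from 0 to 1.4, which is too wide to serve as an estimate.

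**The case against.** The strongest reply is that little is lost. Section 10.4 never says that worsened conditions are exempt, and it requires pre-existing conditions to be recorded, which gives a baseline against which worsening shows. Every adverse event must be recorded, device-related ones reach the sponsor, and 12.2.3 promises individual listings with relationship, severity and outcome, which can be read case by case for ten subjects. The stopping rule in 10.11 does not use SAE status. Much of this stands, and it limits the harm to the SAE count and UADE screening. It does not supply the missing limit, and a site applying the sentence as written would leave the event out of the SAE count.

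A reader might infer four stronger things that the documents do not support:

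- **That the implantation stay has no reference length, so prolongation cannot be judged.** Section 8.1.2 gives one: "Patients will be hospitalized as decided by the surgeon, estimated 1 hospitalization day will be required". It is an estimate at the surgeon's discretion, but it exists, and the criterion asks whether an event prolonged the stay.
- **That an admission to investigate a new infection is exempt as diagnostic.** In the sentence, both diagnostic and elective procedures are tied to pre-existing conditions, and a new infection is not one. Section 10.9.1 also treats specimen collection in active infection as urgent.
- **That glaucoma progression is lost from the UADE count.** It is already listed in 10.8 with an incidence, so it is ordinarily not a UADE whether serious or not. Only an excess over the listed severity or incidence could qualify.
- **That the chance of a missed SAE is 52% to 78%.** Those values are 1 − 0.93^10 = 0.516 and 1 − 0.86^10 = 0.779. They give the chance of at least one glaucoma progression in ten subjects, using rates from another device, and say nothing about elective admission.

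**Conclusion.** The point holds as a defect in a stated rule. Applied as written, 10.4 takes SAE status under the hospitalisation criterion from a pre-existing eye condition that worsened after implantation and led to an elective or diagnostic admission. SAE incidence may therefore be undercounted, by 10 percentage points for each subject so reclassified. That it will be undercounted, or by how much in total, cannot be shown from the protocol.

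The conclusion assumes that sites follow the wording literally and that the event meets no other seriousness criterion. The primary safety endpoint is largely protected, because treatment-related events count there regardless of seriousness. The change is worth making because the study is a ten-subject safety study, SAE incidence is one of its named outputs, and the correction is cheap.

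**What to change.** Amend 10.4 in two respects:

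1. Limit the exemption to admissions for a pre-existing condition that has not worsened since day 0.
2. State that an adverse event that requires or prolongs hospitalisation, including worsening of a pre-existing condition of the study eye, is an SAE even if the procedure is elective or diagnostic.

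The exemption should not be made to depend on the procedure having been planned before implantation. That would turn an elective admission scheduled later for a stable, unrelated condition into an SAE, and so overcount.

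The cost is one or two sentences in an amendment and a possibly slightly less favourable SAE count. No new eCRF field is needed. The change affects classification only, not how any subject is treated or how long anyone stays in hospital.

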# 5.2 Endpoints

# 5.2.1 Primary Safety Endpoint

The frequency and severity of all unanticipated adverse device-related events (UADE) or treatment-related adverse events, during and after implantation of the CorNeat KPro device up to 12 months should be less than SOC (as detailed in section Known Potential Risks).

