#### 7.2.2 Exclusion Criteria

- 7.2.2.1 Reasonable chance of success with traditional keratoplasty
- 7.2.2.2 Current retinal detachment
- 7.2.2.3 Connective tissue diseases
- 7.2.2.4 End stage glaucoma
- 7.2.2.5 History or evidence of severe inflammatory eye diseases (i.e. uveitis, retinitis, scleritis) in one or both eyes within 6 months prior to planned implantation
- 7.2.2.6 History of ocular or periocular malignancy
- 7.2.2.7 History of extensive keloid formation
- 7.2.2.8 Any known intolerance or hypersensitivity to topical anaesthetics, mydriatics, or component of the device
- 7.2.2.9 Signs of current infection, including fever and current treatment with antibiotics
- 7.2.2.10 Severe generalized disease that results in a life expectancy shorter than a year

UNCONTROLLED WHEN PRINTED

**CONFIDENTIAL** - THIS DOCUMENT CONTAINS CONFIDENTIAL AND PROPRIETARY INFORMATION. THIS DOCUMENT MAY NOT BE REPRODUCED, USED, OR DISCLOSED TO ANY THIRD PARTY WITHOUT PRIOR WRITTEN CONSENT.

- 7.2.2.11 Any clinical evidence that the investigator feels would place the subject at increased risk with the placement of the device
- 7.2.2.12 Corneal thickness less than 400 or higher than 1,200 microns in any region of the pachymetry map of the eye intended to be operated
- 7.2.2.13 Currently pregnant or breastfeeding
- 7.2.2.14 Participation in any study involving an investigational drug or device within the past 30 days or 5 half-lives of the drug (whichever longer) or ongoing participation in a study with an investigational drug or device
- 7.2.2.15 Intraoperative complication that would preclude implantation of the study device.
- 7.2.2.16 Vulnerable populations.

Subjects who meet all inclusion criteria and none of the exclusion criteria will be enrolled in the protocol study and implanted with the CorNeat KPro device.

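### Section 10.4 lets glaucoma progression be left out of the trial's device-effect count, while the 10.8 benchmark for the primary safety endpoint counts it

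*Protocol*

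**What the plan says.** The primary safety endpoint in section 5.2.1, repeated in the synopsis, is "The frequency and severity of all unanticipated adverse device-related events (UADE) or treatment-related adverse events" up to 12 months. The criterion is that these "should be less than SOC (as detailed in section Known Potential Risks").

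Section 10.8 opens its list with "Known risks from usage of similar artificial corneas are". Under post-operative glaucoma it gives three separate figures: pressure elevation in 19–38%, "progression of pre-operative glaucoma in 7–14 % of patients", and de novo glaucoma in 2–28%. None carries a stated restriction to events that an investigator attributed to the device.

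Section 10.4, within the definition of a serious adverse event, makes an exception for "changes related to the underlying disease or medical conditions that are consistent with expected disease progression and will not be considered adverse device effects". It does not say how expected progression is to be judged, and it does not define an adverse device effect.

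Eyes with glaucoma can be in the trial. The only glaucoma exclusion in 7.2.2 is "End stage glaucoma", and the pressure instructions in 8.1.6 foresee such patients: "Palpation directly over a glaucoma drainage device plate should be avoided in patients with tubes".

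**The concern.** A comparison with an external benchmark is fair only if both sides count events by the same rule. Here the benchmark includes worsening of a disease that was present before surgery. The trial side has a rule under which the same worsening can be classed as not a device effect. The effect runs one way: it can lower the trial count and cannot raise it.

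What is at stake is the primary safety comparison on one listed component, in a field that 10.8 itself ranks as the leading threat to keeping vision after this kind of surgery. With one arm there is no concurrent control group classified by the same investigators under the same rule, so the bias does not cancel.

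**Working it through.** The protocol sets no alpha, power or margin, and 10 subjects is a non-statistical choice, so there is no stated figure to reproduce. The check is one of definitions, followed by arithmetic for scale.

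**Tracing one event.** Take an eligible eye with glaucoma short of end stage that progresses after implantation.

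1. *Benchmark side.* Section 10.8 counts it: progression of pre-operative glaucoma, 7–14%.
2. *Trial side, as a UADE.* Section 10.5 covers only serious effects not already identified in 10.8 by nature, severity or incidence. Progression at its listed severity and incidence is already identified there, so this route is closed.
3. *Trial side, as a treatment-related adverse event.* This is the remaining route. If the investigator judges the progression expected, 10.4 says it is not an adverse device effect. No section exempts the 10.8 event types from that rule.
4. *Against 10.3.* Not Related requires that the event be clearly due to other factors, such as the subject's clinical state. Possibly Related covers an event with a reasonable temporal link and a known response pattern where another cause may be responsible. Glaucoma progression after a keratoprosthesis fits the second description. Section 10.4 asks only that the change fit expected progression, which is a lower bar than clearly due to other factors. The two sections can therefore classify the same event differently, and the protocol does not say which prevails.

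**Scale.** Inputs: n = 10 (synopsis and 7.1); p = 0.07 and 0.14 (10.8). Assumption A: the rate applies to all 10 eyes over 12 months.

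- Expected events = n × p: 10 × 0.07 = 0.7; 10 × 0.14 = 1.4.
- P(at least one) = 1 − (1 − p)^10: 1 − 0.93^10 = 1 − 0.484 = 0.516; 1 − 0.86^10 = 1 − 0.221 = 0.779.

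If a share m of the events is classed as expected progression, the chance of a trial count of zero is (1 − p(1 − m))^10:

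| Share removed, m | p = 7% | p = 14% |
|---|---|---|
| 0 | 0.484 | 0.221 |
| 0.5 (assumption) | 0.965^10 = 0.700 | 0.93^10 = 0.484 |
| 1 (worst case) | 1 | 1 |

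**If only eyes with prior glaucoma are at risk.** Suppose 5 of the 10 eyes have it and 7–14% is the rate among them (both assumptions). Expected events fall to 5 × 0.07 = 0.35 and 5 × 0.14 = 0.70. P(at least one) becomes 1 − 0.93^5 = 0.304 and 1 − 0.86^5 = 0.530. The counts shrink; the difference in counting rule stays.

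**The case against.** The other side has several sound points.

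- *The exemption is conditional.* It needs a judgement that the course was expected, and 10.6 still requires relatedness to be assessed by the 10.3 definitions. A reader might infer that 10.4 overrides 10.3 whatever category is chosen. The protocol does not say so. What stands is that the two conflict and no precedence is given.
- *The terms differ.* The endpoint speaks of treatment-related events and 10.4 of adverse device effects. Equating them is an inference, though the natural one.
- *The events are not lost.* Section 10.1 requires every adverse event to be recorded whatever its relationship, 12.2.3 lists them individually, and a DSMB reviews the data. With 10 subjects each case can be found. Section 8.1.6 does limit collection at unscheduled visits to related or possibly related events, SAEs and UADEs, but scheduled visits carry no such limit. A reader might infer that nothing else in the trial could reveal the omission; the listings show otherwise.
- *The figures are soft.* Section 10.8 gives no time horizon for the 7–14%, and the number of eyes with prior glaucoma is unknown. A count of zero is certain only if every progression is judged expected. Whether the cited series filtered by attribution cannot be seen from the protocol.
- *There is no formal test to overturn.* The study applies no statistical methods, and no component-level pass rule exists.

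It is also tempting to extend the point to corneal melt (up to 30%) and raised pressure (19–38%). Section 10.8 presents both as postoperative complications, not as worsening of prior disease, and nothing in the protocol calls melt the expected course of Stevens-Johnson syndrome, pemphigoid or burns. The point does not reach that far.

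These arguments limit the size and reach of the problem. They do not remove the mismatch for glaucoma progression, because listing an event does not put it into the endpoint count.

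**Conclusion.** The point holds for progression of pre-operative glaucoma. Section 10.4 permits its omission from the trial side of a comparison whose benchmark includes it; it does not require the omission. The direction favours the device. The size cannot be fixed from the protocol. Under assumption A it concerns about one event in 10 eyes (0.7–1.4), and fewer if only eyes with prior glaucoma are at risk.

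The conclusion rests on two readings: that adverse device effects feed the treatment-related events in 5.2.1, and that the 10.8 rate is unfiltered, since no filter is stated. It should be fixed because it affects the primary safety comparison. It does not call the collected data into question.

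**What to change.** 1. In 10.4, state that the disease-progression exemption does not apply to study-eye events of a type listed in 10.8, and that 10.3 governs their relatedness.
2. In 5.2.1 and the synopsis, state that the comparison with 10.8 uses all study-eye events of the listed types after implantation, regardless of attribution. Report the investigator's attribution, including a judgement of expected progression, in a column alongside.

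The cost is an amendment to the wording of 10.4, 5.2.1 and the synopsis, with matching CRF guidance and the ethics approval that 12.5 requires for any amendment. No new data are needed. The drawback is that the count set against the benchmark may be higher and may include some natural progression; the attribution column lets a reader see how much. The second step does change what is counted in the comparison, so it should be described as an endpoint clarification and not as a correction of wording alone.
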